5.1 Inclusion Criteria

- Adults of 18 years or older
- Patients hospitalized with a diagnosis of COVID-19 based on central laboratory-confirmed COVID-19 Novel Coronavirus Disease-2019, based on a positive SARS-CoV-2 RT-PCR confirmed **within 72 hours** prior to enrollment of nasal, oropharyngeal, or BAL specimen with hypoxemia, (i.e., decrease in oxygenation, as outlined below)
- Pulse oximetry saturation (SpO₂) < 93% on room air in WHO COVID-19 ordinal scale 3 patients, regardless the need for assisted ventilation, or oxygenation.
- Any new requirement of supplemental oxygen, with any oxygen device (WHO COVID-19 ordinal scale 4-7, regardless of pulse oximetry reading)
- In patients with supplemental oxygen at home, **any increase** in the requirement of supplemental oxygen.
- In ICU level of care

5.3.1 Special Considerations: Minorities

The study will emphasize recruitment of ethnic minorities and patients over 65. Specifically, a Spanish language consent will be available, and 24-hour real-time translation services. Furthermore, an attempt will be made to obtain consent and agreement with prison warden in the Richmond region. Once approval has been signed from prison leadership and the local IRB, inmates may be enrolled as well.

5.3.2 Special Considerations: Chronic Kidney Disease and Acute Kidney Injury patients

Special consideration will be given to avoid excluding patients with acute kidney injury (AKI). Recent evidence suggests that AKI develops in up to 60% of high-risk COVID-19 patients. (33) The receptor for SARS-CoV-2 is ACE2 receptor, which is expressed in kidney much more so than in lung. (33) Autopsy studies in COVID-19 demonstrated acute proximal

tubular injury, and peritubular erythrocyte aggregation and glomerular fibrin thrombi with ischemic collapse. (33) Therefore, we have the following provisions:

[figure not shown]
- Exclude patients with KDIGO CKD stage 4 (eGFR < 30 ml/min) or worse. That means patients with KDIGO CKD stage 5 and/or any form of dialysis at baseline are also excluded.
- Exclude patients with pre-existing AKI, stage 3
- Immediate reduction of each infusion dose by 50% if patients develop KDIGO defined AKI stage 2 or higher, until the AKI resolves completely. If the AKI resolves completely, normal dosing can be resumed.
- All AKI and CKD definitions are following the 2012 KDIGO guidelines: Khwaja, A. (2012). KDIGO clinical practice guidelines for acute kidney injury. *Nephron Clinical Practice*, 120(4), c179-c184.

Acute Kidney Injury (AKI) Definitions per KDIGO guidelines

Khwaja, A. (2012). KDIGO clinical practice guidelines for acute kidney injury. *Nephron Clinical Practice*, 120(4), c179-c184.

Stage	Serum creatinine	Urine output
1	1.5–1.9 times baseline OR ≥0.3 mg/dl (≥26.5 µmol/l) increase	<0.5 ml/kg/h for 6–12 hours
2	2.0–2.9 times baseline	<0.5 ml/kg/h for ≥12 hours
3	3.0 times baseline OR Increase in serum creatinine to ≥4.0 mg/dl (≥353.6 µmol/l) OR Initiation of renal replacement therapy OR, In patients <18 years, decrease in eGFR to <35 ml/min per 1.73 m ²	<0.3 ml/kg/h for ≥24 hours OR Anuria for ≥12 hours

Furthermore, we plan daily assessments of renal safety, including daily creatinine, oxalate, and frequent urine oxalate measurements as outlined in detail in the SoA table on page 7. If patients develop AKI, stage 2 or 3 during the first 7 days of the study (4 days of infusion or 3 subsequent days) the following algorithm will be implemented:

If new AKI develops: Plan daily creatinine measurement until improvement in the serum creatinine or urine output occurs for two consecutive days, at which time less frequent assessment as currently proposed in the study protocol can be undertaken.

5.3.3 Patients receiving are receiving therapeutic fluphenazine.

Patients who are taking fluphenazine (e.g., Poloxin) will be excluded.

5.3.4 Special Considerations: Obese patients

Average body weight adults using the VCU protocol for intravenous vitamin C infusion receive 14 – 16 grams of vitamin C infused over a 24-hour period. Because the obese population of patients are known to be at high risk of COVID-19 pneumonia developing into serious respiratory failure we will set a **daily ceiling of 15 grams** infused into patients with BMIs of 40 or above.

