The participant duration will be 90 days. Participants will receive the 4-day treatment period (96-hour); if needed, the last study-specific blood work will be collected up to 7 days follow-up after enrollment. Data up to 28 days follow-up will be collected from medical records, standard of care procedures, and chart review. Follow up data and patient-reported outcome measures will be collected by phone visit at day 90.

Schema

Schedule of Activities (SoA)

Assessments	Day 0-1	Day 1-2	Day 2-3	Day 3-4	Day 5-7**	Day 8-14**	Day 15-21**	Day 22-28**	Day 60&90
WHO-COVID-19 SCALE	R	R	R	R	R	R*	R*	R*	
AKI, present and stage of AKI	R	R	R	R	R	R*	R*	R*	
Creatinine, serum (BMP also includes sodium, chloride, potassium, BUN, bicarbonate, glucose)	R	R	R	R	R	R*	R*	R*	
Fluid Balance and Urine Output	R	R	R	R	R	R*	R*	R*	
Microscopic urine analysis	R	R	R	R	R	R14 ^{AKI}	R21 ^{AKI}	R28 ^{AKI}	
Serum oxalate	R	R	R	R	R	R14 ^{AKI}	R21 ^{AKI}	R28 ^{AKI}	
Random urine oxalate	R	R	R	R	R				
24-hour urine oxalate collection					R5, R7	R14	R21 ^{AKI}	R28 ^{AKI}	
Alive and Free of ANY Respiratory Failure (yes/no)	R	R	R	R	R	R	R	R	
Alive and Free from INVASIVE mechanical ventilation (yes/no)	R	R	R	R	R	R	R	R	
Oxygen Device Oxygen Flow Air Flow [HFNC only] FiO2 [if not NC] Intubated last 24 hours? Date & time of last intubation Extubated last 24 hours or last week? Date & time of last Extubation ECMO	S	S	S	S	S	S	S	S	
Body Weight (kg)	S	S	S	S	S	S	S	S	

	Vital Signs, Mental Status, qSOFA	S	S	S	S	S	S	S	S	
	Maximum norepinephrine rate today	S	S	S	S	S	S	S	S	
	Maximum vasopressin rate today	S	S	S	S	S	S	S	S	
	Maximum dobutamine rate today	S	S	S	S	S	S	S	S	
	Had Cardiac Arrest today (or last week)?	S	S	S	S	S	S	S	S	
	Demographics Comorbidities Active Diagnoses Admission APR-DRG On O2 at home Y/N O2 liters at home Baseline creatinine Baseline CKD stage	S								
	Received Dialysis last 24 hours or last week	S	S	S	S	S	S	S	S	
	Received CRRT last 24 hours or last week	S	S	S	S	S	S	S	S	
	Any episode of hypoglycemia last 24hours and week [Glucose < 50]	S	S	S	S	S	S	S	S	
	Any clinical symptoms of kidney stones? Back pain, Flank pain Hematuria Visible stone passed Imaging consistent with new kidney stone	R	R	R	R	R	R	R	R	
	Today's CBC, Differential	R	R	R	R	R	R	R	R	

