4.1 Overall Design

1. A phase 2, two-center, prospective, randomized, double blind placebo-controlled safety clinical trial.
2. A maximum of 60 patients will be enrolled.
3. Participants will be randomized to receive either intravenous Vitamin C (mixed in 5% dextrose in water) or placebo (5% dextrose in water) in a 1:1 manner.
4. Active treatment will continue for 96-hour period or consent withdrawal or loss to follow-up. One-fourth of the 24-hour calculated dosage will be administered **in 30-minute intravenous infusions of 50 mg/kg and occur every 6 hours** for a total of sixteen 30-minute infusions. **That is 200 mg/kg total per day for 4 days.** The standard of care therapy will be followed. All COVID-19 known therapies will be allowed.
5. All participants will be followed for a total of 28 days on the first phase of the trial and at 60 and 90 days on the second phase.
6. All participants, without exception, will receive the standard of care for COVID-19 including the use of remdesivir, dexamethasone, plasma and other, as a component of standard of care for patients hospitalized with severe disease, in settings where remdesivir is available via the emergency use authorization mechanism.

Analysis/Interim Monitoring:

1. **Only reasons for study withdrawal are withdrawal of consent and, or loss to follow-up**
2. The DSMB will review all SAEs in a narrative and qualitative fashion (not only quantitative), to avoid underpowered statistical misconceptions.
3. Protocol compliance will be monitored by the study team daily discussion. This will take place via investigator conference call and will address challenges encountered. Trial progress will be monitored by an independent Data and Safety Monitoring Board (DSMB) to determine if the study should stop for safety reasons.

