4.3 Justification for Dose

Dosing and bio-distribution data in humans show that pharmacological concentrations of vitamin C can only be attained following intravenous administration. (29) Oral doses cannot achieve therapeutic plasma concentrations. (34-35) Dosage selection for this trial was determined both from animal modeling, examining the biological effectiveness in a lung injury model system and from the recently conducted randomized double-blind phase 2 human ARDS (CITRIS-ALI) trial. (11) **The 200 mg/kg/24-hour IV (50 mg/kg IV every 6 hours)** dosing protocol was determined from analysis of the CITRIS-ALI (200mg/kg IV levels, that was 50 mg/kg IV every 6 hours) plasma ascorbate levels. **A special consideration is given for patients who will develop KDIGO definition AKI, stage 2 or 3 after the infusion. In this scenario, the dosage will be reduce by 50%, for each subsequent**

infusion, until the AKI resolves completely. We are using a dosing ceiling of 15 grams per day, for consideration of vitamin C dosages in obese population. Under no circumstance an individual infusion dose will exceed 3.75 grams of vitamin C, or the daily infused dose above 15 grams.

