6.1.1 Dosing and Administration

- First study drug dose (L-ascorbic acid, 50 mg/kg infusion over 30 minutes) will be considered "Dose 1" and will be administered within the first 8 hours of enrollment or

the earliest available time post any clinically indicated procedure which requires the patient to be off the unit. Doses will be administered in the ED, medicine inpatient unit or ICU. Patients receiving vitamin C will receive 25% of the total daily calculated dosing (200 mg/kg/24 hours) infused over 30 minutes every 6 hours for 96 hours.

- Subsequent doses will be **50 mg/kg infused over 30 minutes every 6 hours.**
 - Timing of Dose 2 will be triggered by the physician order for every 6-hour administration and will, therefore, be listed on the bedside medical administration record (MAR). As such, the timing of Dose 2 may be out of the +/- 3-hour window and will not trigger a protocol deviation.
 - If for any reason any other maintenance dose is not administered within the window, the dose will be skipped, and the next scheduled dose will be given and documented in the data collection tool.

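### The 15 g/day ceiling is unconditional in sections 4.3 and 6.2.4, set for BMI 40 or above in 5.3.4, and absent from the dosing text, so the dose above 75 kg is not uniquely defined

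*Combined protocol and SAP*

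**What the plan says.** **Unconditional ceiling.** Section 4.3 reads: "Under no circumstance an individual infusion dose will exceed 3.75 grams of vitamin C, or the daily infused dose above 15 grams". Section 6.2.4, the pharmacy preparation instruction, repeats that sentence. Neither place attaches a BMI condition to it. In 4.3 the sentence before it gives the motive: "We are using a dosing ceiling of 15 grams per day, for consideration of vitamin C dosages in obese population".

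**Ceiling tied to BMI.** Section 5.3.4 sets a 15 g daily ceiling for doses "infused into patients with BMIs of 40 or above". It gives no per-infusion figure. It also says that adults of average weight treated under the institution's vitamin C protocol "receive 14 – 16 grams of vitamin C infused over a 24-hour period".

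**No ceiling.** Section 4.1 gives 50 mg/kg per infusion and sums it up: "That is 200 mg/kg total per day for 4 days". Section 6.1.1, the dosing section, has each patient on active drug receive "25% of the total daily calculated dosing (200 mg/kg/24 hours) infused over 30 minutes every 6 hours for 96 hours", with later doses of "50 mg/kg infused over 30 minutes every 6 hours". The synopsis objective and section 4.4 also state 50 mg/kg per infusion. None of these four places mentions a maximum.

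**Kidney-injury reduction.** Sections 4.3 and 5.3.2 halve each infusion after new AKI of stage 2 or worse. Neither says whether the half is taken before or after the ceiling is applied.

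**The concern.** A weight-based dose with a fixed maximum is really two regimens: mg/kg below the threshold weight and a flat dose above it. The reader has to know who falls under the maximum, and the protocol answers this in three ways. A BMI threshold has a function only if patients below it are treated differently, yet the sentence in 4.3 and 6.2.4 leaves no room for that. The dosing section read alone has no maximum.

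This matters more here than in most trials because exposure is what is under test. The objective is the safety of a named dose. Section 4.2 says the study explores renal harm, and section 2.2 identifies oxalate nephropathy as the gap in knowledge. Oxalate measurements and AKI-free days are secondary safety endpoints. With at most 30 patients on active drug, a safety statement needs a clear account of what dose was given.

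**Working it through.** **Inputs**
- Dose per infusion: 50 mg/kg, four times a day (4.1, 6.1.1).
- Daily dose: 200 mg/kg (4.1, 6.1.1).
- Ceiling: 3.75 g per infusion, 15 g per day (4.3, 6.2.4); 15 g per day at BMI 40 or above (5.3.4).
- Dose cited for adults of average weight: 14 to 16 g per day (5.3.4).
- Weight and height: assumed. The documents give no distribution, so a range is shown.

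**Step 1: the plan's own figures.** 4 × 3.75 g = 15 g, so the two ceilings agree with each other. 4 × 50 mg/kg = 200 mg/kg, so the two weight-based statements also agree.

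**Step 2: where the ceiling binds.** 15,000 mg ÷ 200 mg/kg = 75 kg, and 3,750 mg ÷ 50 mg/kg = 75 kg.

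**Step 3: the range in 5.3.4.** 14,000 ÷ 200 = 70 kg and 16,000 ÷ 200 = 80 kg. The threshold of 75 kg lies inside the range that the section links to average weight. The part of the range above 15 g exceeds the unconditional ceiling.

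**Step 4: who is affected.** At 75 kg, BMI reaches 40 only at a height of √(75/40) = 1.37 m. Anyone taller has a band of weights, from 75 kg up to the weight at BMI 40, in which the two rules differ. At 1.75 m the band ends at 40 × 1.75² = 122.5 kg.

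**Step 5: size of the difference when BMI is below 40.** With the ceiling for all, the dose is min(0.2 g/kg × weight, 15 g). With the ceiling applied from BMI 40, it is 0.2 g/kg × weight.

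| Weight | Ceiling for all (g/day) | Ceiling from BMI 40 (g/day) | Excess over capped dose | Shortfall from uncapped dose | mg/kg per infusion if capped |
|---|---|---|---|---|---|
| 80 kg | 15 | 16.0 | 7% | 6% | 46.9 |
| 100 kg | 15 | 20.0 | 33% | 25% | 37.5 |
| 122.2 kg | 15 | 24.4 | 63% | 39% | 30.7 |

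The last row is a patient of 1.75 m at BMI 39.9: 39.9 × 1.75² = 122.2 kg; 122.2 × 0.2 = 24.4 g; 24.4/15 = 1.63; 1 − 15/24.4 = 0.39. Also at BMI 39.9, the excess over the capped dose is 45% at 1.65 m (21.7 g) and 82% at 1.85 m (27.3 g).

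**Step 6: the AKI reduction.** For a 100 kg patient under the ceiling, half of the capped infusion is 3.75/2 = 1.875 g. Half of the weight-based infusion is 5/2 = 2.5 g, which is itself below 3.75 g. The text does not say which is meant.

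**The case against.** The strongest reply is that there is no true conflict. Section 5.3.4 does not confine the ceiling to BMI 40 or above; it sets a limit for that group and is silent on the rest. A limit for some and a limit for all can be obeyed together. The unconditional limit also stands in 6.2.4, where the volume for each bag is worked out, so it may well be what is applied. The 14 to 16 g figure can be read as background on usual practice rather than an instruction for this trial.

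Part of this stands. A reader might infer that 5.3.4 exempts everyone below BMI 40, but the section does not say so. On the harmonising reading, though, the BMI threshold does nothing, and the objective and sections 4.1, 4.4 and 6.1.1 still state a dose that patients above 75 kg do not receive.

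Other stronger readings also go beyond the documents:
- *The same patient's dose differs by more than half.* This is true only as an excess over the capped dose, above 112.5 kg (22.5/15 = 1.50), with BMI below 40 and hence a height above √(112.5/40) = 1.68 m. Measured as a cut from the uncapped dose, it passes half only above 150 kg, which at BMI below 40 needs a height above √(150/40) = 1.94 m.
- *Many ordinary adults are affected.* No weight or BMI distribution is given, so the number cannot be stated.
- *The two sites will dose differently.* Nothing shows that sites or pharmacies follow different passages. Randomisation is also blocked by site (6.3), so such a difference would complicate the description of dose rather than bias the comparison of arms.
- *The safety result could not be tied to any dose.* Body weight is in the schedule of activities, drug logs are reviewed (6.4) and plasma ascorbate is measured serially, so delivered mg/kg should be recoverable.

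**Conclusion.** The point holds as an internal inconsistency in the stated dose. Taken together, the passages do not fix one dose for a patient above 75 kg with BMI below 40. The gap runs from 7% of the capped dose at 80 kg to 33% at 100 kg and 63% at 122 kg (1.75 m, BMI 39.9). These sizes follow from the protocol's own dose and ceiling. How many patients fall in the band rests on a weight distribution that the documents do not give.

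The need to act does not depend on which reading prevails. If the ceiling applies to all, the stated 50 mg/kg is not the regimen tested in patients above 75 kg. If it applies from BMI 40, the sentence in 4.3 and 6.2.4 is wrong as written. Divergent dosing is a risk created by the wording and has not been shown to occur. No view is taken here on which rule is right.

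**What to change.** Reconcile the synopsis objective and sections 4.1, 4.3, 4.4, 5.3.4, 6.1.1 and 6.2.4 to a single statement of whom the ceiling applies to, and use the same words in each place. In 4.3 and 5.3.2, say how the 50% AKI reduction relates to the ceiling. Describe the tested regimen in the objective to match. Record the delivered dose in mg per infusion and mg/kg, and report it for the active arm. The choice of rule belongs to the investigators and the regulator.

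The cost is a protocol amendment of wording. Section 6.2.4 already requires the volume for each bag to be calculated, and weight is already scheduled, so reporting delivered mg/kg needs no new measurement. Sample size and the planned tests are unchanged.

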5.4 Screen Failures

Screen failures are defined as participants who consent to participate in the clinical trial but are not subsequently randomly assigned to the study intervention or entered in the study. Effort will be made to collect enough data from screen fails to meet the Consolidated Standards of Reporting Trials (CONSORT) publishing requirements and to respond to queries from regulatory authorities. Minimal information includes demography, screen failure details, eligibility criteria, and any Serious Adverse Event (SAE).

Individuals who do not meet the criteria for participation in this trial (screen failure) because of exclusion criteria such as failure to obtain consent, inability to locate legally authorized representative (LAR), or delay in diagnosis may be rescreened. Rescreened participants should be assigned the same participant number as for the initial screening.

5.5 Strategies for Recruitment and Retention

Non-intubated patients with COVID19 will be recruited from the Emergency Department (ED), the medicine inpatient wards, and the intensive care units (ICU) at VCU Medical Center and the Central Virginia VA Health System in Richmond, Virginia (RICVA). Both institutions are tertiary care medical centers with a large referral base. Study personnel will review patients within the electronic medical record to identify potential candidates for enrollment. Permission to approach patients and/or their families will be requested from the attending physicians in charge of patient care in the ED, inpatient unit, or the ICU. All patients meeting the inclusion/exclusion criteria will be approached with consent and will be entered into a screening log. If the patient is not enrolled, the screening log will include information explaining why enrollment did not occur (exclusion criteria, attending physician denial, patient refusal, etc.).

6 - Study Intervention

6.1 Study Intervention Description

All study drug doses will be administered via central or peripheral line infusion. Should no central or peripheral line be available at the scheduled time of infusion, a call should be placed to the pharmacy to determine if the study drug may be co-infused into the line that is infusing a different drug. If administering a study drug via co-infusion is contraindicated, then study drug infusion may be delayed by a maximum of 8 hours (the nursing assessments in COVID-19 patients are done every 4 hours). If the clinical drug administration schedule is such that the study drug will not have an available administration time beyond this delay, a dedicated new intravenous line (peripheral) should be inserted. Study drug will be blinded using an identical appearing placebo.

6.1.1 Dosing and Administration

- First study drug dose (L-ascorbic acid, 50 mg/kg infusion over 30 minutes) will be considered "Dose 1" and will be administered within the first 8 hours of enrollment or

the earliest available time post any clinically indicated procedure which requires the patient to be off the unit. Doses will be administered in the ED, medicine inpatient unit or ICU. Patients receiving vitamin C will receive 25% of the total daily calculated dosing (200 mg/kg/24 hours) infused over 30 minutes every 6 hours for 96 hours.

- Subsequent doses will be **50 mg/kg infused over 30 minutes every 6 hours.**
 - Timing of Dose 2 will be triggered by the physician order for every 6-hour administration and will, therefore, be listed on the bedside medical administration record (MAR). As such, the timing of Dose 2 may be out of the +/- 3-hour window and will not trigger a protocol deviation.
 - If for any reason any other maintenance dose is not administered within the window, the dose will be skipped, and the next scheduled dose will be given and documented in the data collection tool.

6.1.2 Concurrent Medication Infused and Renal Acidification

Urine pH will be monitored daily according to the Scheduled of Activities table.

Fluoroquinolones, aminoglycosides, macrolides function optimally at alkaline pH.

Tetracyclines, nitrofurantoin, many β -lactams exhibit highest activity under acidic conditions.

Sulfamethoxazole, oxacillin, amoxicillin and clavulanic acid, vancomycin, imipenem, and clindamycin are unaffected by pH. (32) See section 6.5.2 for a detailed list of all known medication interactions.

6.2 Preparation/Handling/Storage/Accountability

6.2.1 Acquisition and accountability

VCU Health and the VA Investigational Drug and/or Inpatient Pharmacy will coordinate the acquisition of sterile L-ascorbic acid (Ascor®) for infusion from McGuff Pharmaceuticals, Santa Ana, CA.

6.2.2 Formulation, Appearance, Packaging, and Labeling

Ascor vials contain 25,000 mg/50 mL of pH-balanced ascorbic acid and is supplied as pharmacy bulk packaging (PBP). The diluted Ascor solution is colorless to pale yellow. The placebo will be 50 ml Dextrose 5% Water (D5%W). **Sealed amber shrouding will be used to cover the IV bag in order to maintain the blind.**

